8.1.6. Prior and Concomitant Medications

Prior IBS medications and ongoing (concomitant) medications will be recorded beginning at the signing of the ICF and continuing until the Safety Follow-up call.

8.2. Efficacy Assessments

Efficacy assessments will be collected as outlined in the Schedule of Assessments ([Section 1.3](#)).

Assessment	Timing	Measurement
Abdominal Pain Intensity (API)	Daily during Run-in and double-blind Treatment Period	
 • 0- to 10-point numeric rating scale: 
 – 0 = no pain – 10 = worst possible pain 
Subjects will record worst abdominal pain on evening Pain Diary in response to daily prompt

PRO Questionnaires	At Baseline and specified visits during double-blind Treatment Period before vital signs and blood draw	
 • GIS • WPAI • IBS-QoL • Additional abdominal pain questions

eCRF = electronic case report form; GIS = Global Improvement Scale; IBS-QoL = IBS quality of life assessment; PRO = patient-reported outcomes; WPAI = Work Productivity and Activity Impairment

8.2.1. Symptom Diaries

Subjects will complete 2 diaries daily, a Bowel Movement Diary and a Pain Diary. The Bowel Movement Diary will be event-driven (ie, subjects will record events as they occur) and will capture bowel movement frequency and form, bowel urgency, and recurrent bowel movements. The Pain Diary will prompt subjects each evening to answer a question regarding worst abdominal pain for the past 24 hours using the 0- to 10-point NRS to rate pain and to capture use of rescue medications.

Subjects will receive the diaries and be trained on their use at the start of the Run-in Period (Visit 2). At subsequent visits, subjects will be re-instructed or retrained as needed. Subjects

must be able to complete the diaries to be eligible for the study. Further details on training and the use of the diaries are provided in a separate manual.

8.2.2. Patient-reported Outcomes

Subjects will complete questionnaires at the site at the start of each required study visit (before vital signs and blood draws) to assess subject-perceived symptom relief and health-related quality of life. The PRO questionnaires are provided in Section □.

8.3. Safety Assessments

Planned timepoints for all safety assessments are provided in the Schedule of Assessments ([Section 1.3](#)). Immediate safety concerns should be discussed with the Sponsor's designated Medical Monitor immediately upon occurrence or awareness to determine if the subject should continue or discontinue study drug.

8.3.1. Physical Examinations

Brief physical examinations will include examination of the heart, lungs, abdomen, visual examination of the external genitalia and perianal area, and any other areas as needed. In addition, any organ system in which a previous abnormality was noted at Baseline or a subject has a complaint or AE will be examined.

8.3.2. Vital Signs

Vital signs, including blood pressure, pulse, body temperature, weight, and height, will be assessed at the timepoints specified in the Schedule of Assessments ([Section 1.3](#)) and [Section 10.7](#) as follows:

- Blood pressure and pulse will be measured after the subject has been resting in a seated position for 5 minutes, after PRO assessments and before any blood draws.
- Blood pressure measurements will be taken on the same arm and by the same site staff throughout the study, if possible.
- Sitting systolic and diastolic blood pressures will be determined by averaging 3 replicate measurements obtained 1 to 2 minutes apart. The average of the 3 measurements will be used for eligibility and safety assessments.
- The same method for assessing temperature should be used at all visits for a particular subject.
- Body weight will be measured with subjects in street clothing with jacket/coat and shoes removed, using the same scale throughout the study, if possible.
- Standing height will be measured without shoes, at Screening only.

8.3.3. *Electrocardiograms*

At Screening only, a 12-lead ECG will be performed in the supine position using an ECG machine that automatically calculates the heart rate and measures PR, QRS, QT, and QTc intervals. ECGs will be read by trained personnel at the study site.

8.3.4. *Clinical Safety Laboratory Assessments*

All protocol-required laboratory assessments, as defined in [Section 10.2](#) and including urine pregnancy test and drug screen, must be conducted in accordance with the laboratory manual and the Schedule of Assessments ([Section 1.3](#)). Repeat or unscheduled samples may be taken for safety reasons or for technical issues with the samples.

The clinical significance of test results will be evaluated as follows:

- At Screening, the Investigator or physician sub-investigator will assess the clinical significance of any values outside the reference ranges provided by the laboratory, and subjects with abnormalities judged to be clinically significant will be excluded from the study.
- The Investigator or physician sub-investigator must review the laboratory report, document this review, and record any clinically relevant changes occurring during the study in the AE section of the eCRF. The laboratory reports must be filed with the source documents. Clinically significant abnormal laboratory findings are those which are not associated with the underlying disease, unless judged by the Investigator to be more severe than expected for the subject's condition.
- All laboratory tests with values considered clinically significant during participation in the study or within 14 days after the last dose of study drug should be repeated until the values return to normal or baseline or are no longer considered clinically significant by the Investigator or Sponsor's designated Medical Monitor.
 - If such values do not return to normal/baseline within a period of time judged reasonable by the Investigator, the etiology should be identified and the Sponsor's designated Medical Monitor notified.
 - If laboratory values from nonprotocol-specified laboratory assessments performed at the institution's local laboratory require a change in subject management or are considered clinically significant by the Investigator (eg, SAE or AE), then the results must be recorded in the eCRF.

8.4. *Adverse Events and Serious Adverse Events*

The definitions of an AE and SAE can be found in [Section 10.3](#).

AEs will be reported by the subject (or, when appropriate, by a caregiver, surrogate, or the subject's legally authorized representative).

The Investigator and any qualified designees are responsible for detecting, documenting, and recording events that meet the definition of an AE or SAE and remain responsible for following up AEs that are serious, considered related to the study drug or study procedures, or that caused the subject to discontinue the study drug or the study (see [Section 7](#)).

8.4.1. Time Period and Frequency for Collecting Adverse Event and Serious Adverse Event Information

All AEs and SAEs will be collected from the signing of the ICF through 14 days after the last dose of study drug. AEs will be collected at the timepoints specified in the Schedule of Assessments ([Section 1.3](#)), and as observed or reported spontaneously by study subjects.

Medical occurrences that begin before the start of double-blind study drug, but after obtaining informed consent, will be recorded in the AE section of the eCRF.

All SAEs (including serious AESIs) will be recorded and reported on the eCRF within **24 hours** of the study site personnel's knowledge of the event, as indicated in [Section 8.4.4](#). Marking the event as "serious" will automatically send required notifications for Sponsor or designee review. The Investigator will also submit any updated SAE data within 24 hours of receipt of the information. Nonserious AESIs will be reported on the eCRF within **72 hours** of the site's knowledge of the information.

Investigators are not obligated to actively seek AE or SAE information after conclusion of the study participation. However, if the Investigator learns of any SAE, including a death, at any time after a subject has been discharged from the study, and he/she considers the event to be reasonably related to the study drug or study participation, the Investigator must promptly notify the Sponsor or designee.

The method of recording, evaluating, and assessing causality of AEs and SAEs and the procedures for completing and transmitting SAE reports are provided in [Section 10.3](#).

8.4.2. Method of Detecting Adverse Events and Serious Adverse Events

Care will be taken not to introduce bias when detecting AEs and SAEs. Open-ended and non-leading verbal questioning of the subject is the preferred method to inquire about AE occurrences.

8.4.3. Follow-up of Adverse Events and Serious Adverse Events

After the initial AE or SAE report, the Investigator is required to proactively follow each subject at subsequent visits/contacts. All AEs will be followed until the Week 14 Safety Follow-up telephone call (14 days [with a -7-day window] after the last dose of study drug). All SAEs will be followed until resolution, stabilization, the event is otherwise explained, or the subject is lost to follow-up (as defined in [Section 7.3](#)). If a subject dies during participation in the study or

within 14 days of the last dose of study drug, the Investigator will provide the Sponsor or designee with a copy of any postmortem findings including histopathology.

The Investigator is obligated to perform or arrange for the conduct of supplemental measurements and/or evaluations as medically indicated or as requested by the Sponsor or designee to elucidate the nature and/or causality of the AE or SAE as fully as possible. This may include additional laboratory tests or investigations, histopathological examinations, or consultation with other health care professionals.

New or updated information will be recorded in the originally completed eCRF. As noted above, the Investigator will submit any updated SAE data within 24 hours of receipt of the information.

8.4.4. Regulatory Reporting Requirements for Serious Adverse Events

- Prompt notification of an SAE by the Investigator to the Sponsor or designee is essential so that legal obligations and ethical responsibilities towards the safety of subjects and the safety of a study drug under clinical investigation are met.
- The Sponsor has a legal responsibility to notify both the local regulatory authority and other regulatory agencies about the safety of a study drug under clinical investigation. The Sponsor will comply with country-specific regulatory requirements relating to safety reporting to the regulatory authority, Institutional Review Board (IRB) or Independent Ethics Committee (IEC), and Investigators.
- Investigator safety reports must be prepared for suspected unexpected serious adverse reactions according to local regulatory requirements and Sponsor policy and forwarded to Investigators as necessary.
- An Investigator who receives an Investigator safety report describing an SAE or other specific safety information (eg, summary or listing of SAEs) from the Sponsor or designee will review and then file it and will notify the IRB/IEC, if appropriate according to local requirements.

8.4.5. Pregnancy

If any subject becomes pregnant during the study (from signing the ICF through 14 days after the last dose of study drug), the site must discontinue the subject from study drug immediately and have the subject return for an Early Withdrawal Visit (Week 12 Visit assessments). The Investigator must inform the subject of the right to receive treatment information. If the subject chooses to receive unblinded treatment information, the individual blind should be broken and the treatment assignment provided to the subject (see [Section 6.3](#) for unblinding information). The study team will remain blinded to the subject's treatment assignment.

In the case of a pregnant subject, if she agrees, the Investigator should notify the subject's primary care physician of the pregnancy and provide details of the subject's participation in the study and treatment (blinded or unblinded, as applicable).

A pregnancy is to be reported to the Sponsor's designated Medical Monitor **within 24 hours of awareness** by the study site personnel using the contact information on the Study Contacts Page and the dedicated pregnancy reporting form. The expected date of delivery or expected date of the end of the pregnancy, last menstruation, estimated conception date, pregnancy result, neonatal data, etc. should be included in this information, as available.

The Investigator will follow the medical status of the mother, the pregnancy, as well as the outcome of the infant at birth, and will report the outcome to the Sponsor or designee.

If the pregnant subject experiences an SAE during pregnancy, or the outcome of the pregnancy meets the criteria for immediate classification as an SAE (ie, spontaneous abortion [any congenital anomaly detected in an aborted fetus is to be documented], stillbirth, neonatal death, or congenital anomaly), the Investigator should follow the procedures for reporting SAEs (ie, report the event on the AE eCRF within 24 hours of the Investigator's knowledge of the event).

All neonatal deaths and congenital anomalies that occur within 30 days of birth (regardless of causality) should be reported as SAEs. In addition, any infant death or congenital anomaly occurring after study completion that the Investigator suspects is related to the in-utero exposure to the study drug should also be reported. Refer to [Section 10.6.2](#) for additional information regarding collection of pregnancy data.

8.4.6. Disease-Related Events and/or Disease-Related Outcomes Not Qualifying as Adverse Events or Serious Adverse Events

No disease-related events or outcomes are excluded from AE reporting. Any worsening of diarrhea or constipation and any new onset of constipation should be collected as AEs.

8.4.7. Adverse Events of Special Interest

Selected nonserious and serious AEs will be reported as AESIs. The events must be reported on the AE eCRF within 24 hours of the study site personnel's knowledge of the event. AESIs that also meet the definition of an SAE must be reported as described in [Section 10.3](#).

Adverse events of clinical interest for this study include:

- Potential major cardiac and cerebrovascular events, including death (or any event with fatal outcome), myocardial infarction, cerebrovascular accident, hospitalization for unstable angina or chest pain, hospitalization for heart failure, and coronary revascularization/angioplasty/stent
- Hypertension, defined as follows:
 - [REDACTED]

- [REDACTED]
- [REDACTED]
- AEs consistent with orthostatic hypotension as confirmed by orthostatic vital signs
- AEs suggestive of cystitis or urinary tract infection (UTI)
- [REDACTED]
- [REDACTED]
- [REDACTED]
- [REDACTED]

- Elevated aspartate aminotransferase (AST) or alanine aminotransferase (ALT) lab value requiring that study drug be temporarily withheld or permanently discontinued (see [Sections 8.4.7.1](#) and [8.4.7.2](#)). To date, no concern regarding drug-induced liver toxicity has been identified; however, the Sponsor is monitoring laboratory data for a potential safety signal, consistent with Food and Drug Administration (FDA) guidance [[FDA Guidance, 2009](#)].

Serious AESIs and elevated liver enzymes or bilirubin requiring withholding of study drug must be reported within 24 hours of the study site personnel's knowledge of the event by marking the appropriate box on the AE eCRF and assigning the most appropriate category. Additional information should be provided as directed in the eCRF Completion Guidelines. AESIs that also meet the definition of an SAE must be reported as an SAE, as described in [Section 8.4.4](#). Nonserious AESIs should be reported within 72 hours of the site personnel's knowledge, using the AE eCRF.

8.4.7.1. Criteria for Temporary Withholding of Study Drug in Association with Liver Test Abnormalities

Elevated liver enzymes or bilirubin sufficient to require withholding study medication must be reported **within 24 hours of the study site personnel's knowledge of the event** using AESI -specific eCRFs/forms/worksheets provided for the study.

Hepatic enzymes will be monitored in accordance with FDA drug-induced liver injury guidelines [[FDA Guidance, 2009](#)].

If **any** of the following liver test abnormalities develop, study drug should be withheld immediately with appropriate clinical follow-up (including repeat laboratory tests, until a subject's laboratory profile has returned to normal/baseline status), and the event reported as an SAE:

- ALT or AST $> 8 \times$ upper limit of normal (ULN)
- ALT or AST $> 5 \times$ ULN and persists for more than 2 weeks
- ALT or AST $> 3 \times$ ULN and total bilirubin $> 2 \times$ ULN or international normalized ratio (INR) > 1.5
- ALT or AST $> 3 \times$ ULN with appearance of fatigue, nausea, vomiting, right upper quadrant pain or tenderness, fever, rash and/or eosinophilia ($> 5\%$)

Rechallenge may be considered if an alternative cause for the abnormal liver tests (ALT, AST, total bilirubin) is discovered and the laboratory abnormalities resolve to normal or baseline values. The Investigator and Sponsor's designated Medical Monitor must discuss and agree with any decision to rechallenge.

Rechallenge should not occur when the etiology of the liver test abnormalities is considered possibly drug-induced.

8.4.7.2. Criteria for Permanent Discontinuation of Study Drug in Association with Liver Test Abnormalities

Study drug should be discontinued permanently if **all** of the following 4 criteria are met (ie, potential severe drug-induced liver injury/Hy's law case):

- Total bilirubin increases to $> 2 \times$ ULN or INR > 1.5 **and**
- AST or ALT increases to $\geq 3 \times$ ULN **and**
- Alkaline phosphatase value does not reach $2 \times$ ULN **and**
- No alternative cause explains the combination of the above laboratory abnormalities; important alternative causes include, but are not limited to, the following:
 - Hepatobiliary tract disease
 - Viral hepatitis (eg, hepatitis A/B/C/D/E, Epstein-Barr virus)
 - Exposure to hepatotoxic agents/drugs or hepatotoxins, including herbal and dietary supplements, plants, and mushrooms;
 - Alcoholic hepatitis
 - Non-alcoholic steatohepatitis

- Autoimmune hepatitis

If an alternative cause for hepatotoxicity is identified, then it should be determined (based on the severity of the hepatotoxicity or event) whether study drug should be withheld or permanently discontinued as appropriate for the safety of the subject, following consultation with the Sponsor's designated Medical Monitor.

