1.3. Schedule of Assessments

	Screening	Run-in	Double-blind Treatment					Safety Follow-up	Notes
	Visit 1	Visit 2	Visit 3	Visit 4	Visit 5	Visit 6	Visit 7	Telephone Call	
Day/Week	Day -42 to -15	Day -14	Baseline Day 1	Week 2 (Day 15)	Week 4 (Day 29)	Week 8 (Day 57)	Week 12 or Early WD (Day 85)	Week 14 or 14 days after last dose (at the latest)	
Visit Window		± 4 days		± 4 days	± 4 days	± 4 days	± 4 days	-7 days	Safety Follow-up call will occur 7 to 14 days after the last dose of study drug (includes window of -7 days) ^a
Informed consent	X								
Subject entry into IWRS and subject registry	X								
Inclusion and exclusion criteria review	X	X	X						Recheck clinical status before Run-in and randomization
Demographics	X								
Medical history and surgical history	X								Includes current use of illicit drugs, alcohol and caffeine
IBS history	X								Including previous treatments and diets
AE/SAE review	X	X	X	X	X	X	X	X	From informed consent to Safety Follow-up call
Concomitant medication review	X	X	X	X	X	X	X	X	

	Screening	Run-in	Double-blind Treatment					Safety Follow-up	Notes
	Visit 1	Visit 2	Visit 3	Visit 4	Visit 5	Visit 6	Visit 7	Telephone Call	
Day/Week	Day -42 to -15	Day -14	Baseline Day 1	Week 2 (Day 15)	Week 4 (Day 29)	Week 8 (Day 57)	Week 12 or Early WD (Day 85)	Week 14 or 14 days after last dose (at the latest)	
Visit Window		± 4 days		± 4 days	± 4 days	± 4 days	± 4 days	-7 days	Safety Follow-up call will occur 7 to 14 days after the last dose of study drug (includes window of -7 days) ^a
Vital signs	X	X	X	X	X	X	X		Body temperature, blood pressure (avg of 3 results) and pulse after sitting for 5 min and before blood draw: Visits 1 to 7 Weight: Visits 1, 3, and 7 Height: Visit 1
Brief physical examination	X		X				X		Heart, lungs, abdomen, external genitalia, perianal area, and others as needed
Urine β-hCG pregnancy test	X		X				X		Women of child-bearing potential only; serum test required if urine test positive
Urine drug screen	X	X ^c							Refer to exclusion criterion #29 and Section 6.5 for additional details on possible repeat testing at Visit 2 in the event of an initially positive result at Visit 1.

	Screening	Run-in	Double-blind Treatment					Safety Follow-up	Notes
	Visit 1	Visit 2	Visit 3	Visit 4	Visit 5	Visit 6	Visit 7	Telephone Call	
Day/Week	Day -42 to -15	Day -14	Baseline Day 1	Week 2 (Day 15)	Week 4 (Day 29)	Week 8 (Day 57)	Week 12 or Early WD (Day 85)	Week 14 or 14 days after last dose (at the latest)	

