2.3.2. Potential Risks

To date, in subjects (male or female) with overactive bladder, no adverse reactions specific to vibegron have been identified.

Based on aggregate preclinical, clinical pharmacology, and Phase 2 and 3 studies, AEs of special interest (AESIs) predefined for specific evaluations in vibegron clinical studies are as follows:

[figure not shown]
- Potential major cardiovascular events
- Hypertension
- AEs suggestive of orthostatic hypotension
- AEs suggestive of cystitis or urinary tract infection
- Elevated AST or ALT lab value requiring that the study drug be temporarily withheld or permanently discontinued

Prespecified definitions of AESIs are provided in [Section 8.4.7](#). More detailed information about the known and expected benefits and risks and reasonably expected AEs of vibegron may be found in the most recent version of the Investigator's Brochure.

3. Objectives and Endpoints

Objectives	Endpoints
Primary	
To compare the effect of vibegron vs placebo in subjects with abdominal pain due to IBS-D on the API weekly responder rate over 12 weeks
 
 • Proportion of IBS-D subjects who are API weekly responders over 12 weeks 
 - An API Weekly Responder is defined as a subject who experiences a decrease in the weekly average of “worst abdominal pain in the past 24 hours” scores of at least 30% compared with the baseline weekly average
Secondary	
To compare the effect of vibegron vs placebo in subjects with abdominal pain due to IBS-D or IBS-M on patient-reported outcomes
 
 • Proportion of GIS responders at Week 12 for all IBS subjects, including IBS-D and IBS-M subjects

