7.5. Vital Signs

Vital sign data including blood pressure, pulse rate and body temperature will be collected at all study visits except for the safety telephone follow-up visit. Body weight will be measured at Screening, baseline visit and Week 12 and Height will be measured at Screening only. Blood pressure and pulse will be measured in triplicate at each visit. The average of triplicates will be used for summary.

For all parameters, absolute values and change from baseline will be presented for scheduled visits using descriptive statistics for continuous variables. In addition, the maximum post-baseline, change from baseline to the maximum post-baseline, and change from baseline to the end of treatment will be summarized for each of the vital signs.

To further investigate changes in SBP/DBP/pulse rate from baseline, the following tables will be prepared:

- Counts and percent of subjects in each group with at least a 5/10/15 CFB at 3 consecutive post-baseline visits and at Week 12 will be produced for all subjects, by pre-existing hypertension category (Yes/No) and by baseline hypertension category (Yes/No). If the percentage of subjects in a subgroup is less than 25% of the total population, the subgroup in question will be not included in summary
- CFB in Maximum post-baseline (including 95% CI of Mean)

A by-subject listing, sorted by subject identifier, will be presented including all vital sign results (scheduled or unscheduled).

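### The orthostatic hypotension AESI requires a confirmatory reading that the visible plan neither schedules nor triggers, so a low count could not be told apart from a lack of measurement

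*Protocol*

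**What the plan says.** - **Case definition.** Protocol 8.4.7 lists "AEs consistent with orthostatic hypotension as confirmed by orthostatic vital signs" among the AESIs. SAP 7.3 uses the same words. Neither says when or how the orthostatic readings are taken, or what change counts as confirmation.
- **Broader wording elsewhere.** Protocol 2.3.2 lists the same AESI as "AEs suggestive of orthostatic hypotension", with no confirmation. Below its list it adds "Prespecified definitions of AESIs are provided in" Section 8.4.7.
- **What is measured.** Protocol 8.3.2: "Blood pressure and pulse will be measured after the subject has been resting in a seated position for 5 minutes", and "Sitting systolic and diastolic blood pressures will be determined by averaging 3 replicate measurements obtained 1 to 2 minutes apart". The Schedule of Assessments says the same for Visits 1 to 7: "blood pressure (avg of 3 results) and pulse after sitting for 5 min and before blood draw". The visit lists in 10.7 add no standing reading. SAP 7.5 says "Blood pressure and pulse will be measured in triplicate at each visit" and derives no postural-change variable.
- **Room for extra readings.** Protocol 8.4.3 obliges the investigator to "perform or arrange for the conduct of supplemental measurements and/or evaluations as medically indicated", or as the sponsor or its designee requests. Section 4.1 allows unscheduled visits for safety concerns. Neither mentions orthostatic readings.
- **Where the count appears.** SAP Table 14.3.2.1, the overall adverse event summary, shows the AESI categories as subcategories and is a topline output. Table 14.3.2.2, all treatment-emergent events by system organ class and preferred term, is an end-of-study output only.

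**The concern.** An AESI is singled out so that it is reported quickly and read first. Here an event enters the category only if someone took a reading that the visible plan does not ask for. Take a woman who has dizziness on standing at home and is well at her next visit, which may be four weeks later. She has no confirmatory reading and drops out of the category, however typical her symptoms were. Another woman with the same symptoms counts if her site happened to measure her in time. Two sites that both follow the protocol could then report different counts for the same events.

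Adverse events are a secondary endpoint, and the DSMB, whose remit names AESIs, meets three times. A zero or near-zero line in the topline table could be taken as reassurance when it may only mean that nobody measured. An unconfirmed nonserious event also misses the AESI reporting deadline, which is at most 72 hours.

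**Working it through.** The plan gives no rate of orthostatic events and no rate of confirmation, so it has no figure of its own to reproduce. The check is mainly a comparison of text.

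**Step 1. Does any specified procedure supply the confirming reading?**

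| Place | Posture specified | Orthostatic reading |
|---|---|---|
| Schedule of Assessments, Visits 1 to 7 | Sitting | None |
| Protocol 8.3.2 | Seated, mean of 3 sitting replicates | None |
| Protocol 10.7 visit lists | None stated | None |
| Safety follow-up call | Telephone contact | Not possible |
| SAP 7.5 | Triplicate mean | No postural variable |

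Scheduled orthostatic readings: 0 at 7 visits, four of which (Weeks 2, 4, 8 and 12) fall after double-blind dosing starts. Events remain treatment-emergent for 14 days after the last dose, when the only planned contact is the call.

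**Step 2. Is this AESI treated differently from the others?**

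- Urinary tract infection keeps the suggestive wording in 8.4.7 and has a symptom-triggered test: a dipstick at unscheduled visits, then urinalysis and culture if positive (Schedule footnote b; 10.2).
- The liver AESI rests on scheduled chemistry, with repeat testing in 8.4.7.1.
- Hypertension can draw on the seated readings at every visit (its detailed definition is redacted).
- Major cardiac and cerebrovascular events are clinical diagnoses or hospital events.
- Among the visible definitions, only orthostatic hypotension requires a measurement that is neither scheduled nor triggered.

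**Step 3. How does the count respond?** Let n be the women per arm, r the true rate of orthostatic events, and c the share of those events that a site measures and confirms. Then

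expected AESIs = n × r × c, and P(no AESI in the arm) = (1 − r × c)^n.

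n = 100 per arm comes from Protocol 9.2. The values of r and c below are assumptions, not document figures.

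| Assumed r, vibegron vs placebo | Assumed c | Expected AESIs | P(none in vibegron arm) |
|---|---|---|---|
| 5% vs 2% | 1 | 5.0 vs 2.0 | 0.6% |
| 5% vs 2% | 0.5 | 2.5 vs 1.0 | 8% |
| 5% vs 2% | 0.25 | 1.25 vs 0.5 | 28% |
| 5% vs 2% | 0.10 | 0.5 vs 0.2 | 61% |
| 2% vs 1% | 0.25 | 0.5 vs 0.25 | 61% |
| 10% vs 5% | 0.10 | 1.0 vs 0.5 | 37% |

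Worked line: 100 × 0.05 × 0.10 = 0.5 expected, and (1 − 0.005)^100 = 0.61. If c is the same in both arms, the expected ratio is kept but the difference shrinks: 5.0 − 2.0 = 3.0 at c = 1, 1.25 − 0.5 = 0.75 at c = 0.25, and 0.5 − 0.2 = 0.3 at c = 0.10. The table shows how the count behaves. It is not an estimate for this trial.

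**The case against.** The strongest reply has five parts.

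1. **Confirmation follows an event, so it need not be in the routine schedule.** Section 8.4.3 obliges the investigator to arrange extra measurements when indicated, 8.3.1 requires examination of an organ system with a complaint, and unscheduled visits are allowed. This stands against any claim that the count must be near zero whatever the drug does. It does not close the gap: none of these provisions names orthostatic readings, and a woman who has recovered by the time she is seen may never be confirmed.
2. **Section 2.3.2 is a summary list.** A reader might infer that it contradicts 8.4.7. It does not, because it sends the reader there for definitions, and the SAP matches 8.4.7. What remains is a difference in breadth.
3. **The events are not lost.** A reader might infer that a safety signal would vanish. All treatment-emergent events are tabulated by preferred term, all adverse events are listed, and the DSMB's remit covers all other adverse events as well. This stands and limits the harm to the AESI category. However, symptoms may scatter over several preferred terms, and the full table is not a topline output.
4. **Requiring confirmation is a legitimate choice of specificity.** True, and sites are blinded, so nothing suggests that confirmation would differ by arm. Showing confirmed events as a sub-row keeps that specificity.
5. **Text that cannot be seen may hold a procedure.** Parts of 8.4.7 are redacted, and the eCRF Completion Guidelines and DSMB documents are not available. This cannot be excluded. The Schedule, 8.3.2 and 10.7, where such a procedure would normally sit, show no redaction.

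**Conclusion.** The point holds in a limited form. As visibly written, the AESI depends on a reading that the plan neither schedules nor triggers. Its count can be under-ascertained, and a low count could not be distinguished from a lack of measurement. The effect is confined to the AESI category, its expedited reporting and its sub-row in the topline table. The general adverse event tables and the efficacy analyses are unaffected.

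The size of the under-count cannot be derived from the documents. The direction follows from the definition: the count falls in proportion to the share of events confirmed, and reaches zero only if none is. The conclusion assumes that no redacted or separate document instructs sites to take orthostatic readings after a suggestive event. If one does, what remains is the difference in wording between 2.3.2 and 8.4.7.

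**What to change.** - Use one definition in Protocol 2.3.2, Protocol 8.4.7 and SAP 7.3. Report and tabulate as AESIs all adverse events suggestive of orthostatic hypotension.
- Identify them by a preferred-term list fixed before unblinding. The SAP already lists terms for hypertension events and commits to a list for gastrointestinal and IBS-related events. Without such a list, local judgement of what is suggestive would replace local habits of measurement.
- Add a flag to the adverse event form: were orthostatic vital signs taken and, if so, did they confirm the event?
- In the AESI tables, including Table 14.3.2.1, show three sub-rows: confirmed, not confirmed and not measured.

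The cost is a wording change in both documents, a short term list, one form item and three sub-rows. No new patient procedure is needed. This does not fill the measurement gap, but it makes the gap visible. The small downside is that some non-specific dizziness will be counted, which the sub-rows separate from confirmed cases.
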